9.1 Description

The Kronos Electrocautery Device (**Figure 1**) is a disposable electrocautery device that can cauterize deep tissue through a standard biopsy procedure guide needle. This device is intended to coagulate the tissue surrounding the core biopsy channel during withdrawal to reduce or eliminate significant post-procedural bleeding. Currently, the Kronos Electrocautery Device consists of one (1) size. As such, the existing Kronos Electrocautery Device is chosen as the worst-case condition.

Figure 1: Kronos Electrosurgery Device

10 Study Procedures

10.1 Visit 1 (Screening and Enrollment up to the day of Biopsy)

1. Review of the medical record to confirm the patient meets study enrollment criteria
2. Informed Consent - Patients will be identified during their preoperative appointment and introduced to the study; they will be provided with a copy of the consent document and information about the study. The consenting will take place after additional discussion on the day of procedure.
3. Screening will include past and current medical history, a physical examination, blood labs (including Platelet account, INR, Fibrinogen, aPTT and other tests may be considered as needed), and history of current medications. Lab testing is performed prior, as standard of care, to determine if someone may have an undiagnosed bleeding disorder related to their current medical condition prior to participation.

10.2 Visit 2 (Treatment – Day of Biopsy procedure)

1. Ultrasound guided percutaneous biopsy will be performed as per standard of care
2. Placement of the desired core biopsy needle and guide needle will be as per standard of care
3. The needle will be removed, leaving the guide needle in place.
4. Biopsy forceps will be advanced through the guide needle to obtain the tissue
5. The biopsy forceps will be removed with the tissue
6. Remove Kronos Electrosurgery Device from packaging and visually inspect. Record Device Condition score per Attachment 1 – Kronos Scoring Criteria
7. Using the current Instruction for Use (IFU), the Kronos Electrosurgery Device will be advanced to a predetermined length (recorded) to ensure that it protrudes into the biopsy track. Record Maneuverability to Target Tissue score per Attachment 1 – Kronos Scoring Criteria. If Guide needle was used, record Compatibility with guide needle score per Attachment 1 – Kronos Scoring Criteria
8. The Kronos Electrosurgery Device will be activated, and the device and guide needle will

be withdrawn simultaneously at controlled speed. The total time of withdrawal (recorded). Record Withdrawal Force score per Attachment 1 – Kronos Scoring Criteria

9. Any blood or fluids from the access site will be soaked up with a dry gauze without placing any pressure on the access site.
10. Blood or other fluids will be collected for a minimum of five minutes, or until all bleeding has stopped (if applicable). The gauze will be weighed (recorded) to estimate the blood loss with results. Record Device Performance (Blood control) score per Attachment 1 – Kronos Scoring Criteria.
11. This procedure will be performed a single time, on areas that include, but are not limited to, liver, kidney, lungs, breasts, soft tissue, etc.,.. The biopsy procedure is being performed as a standard of care, which may require multiple passes.

10.3 Schedule of Events

Study Activity	Schedule of Events		
	Screening/Baseline	Procedure	Follow-up
Informed consent	X		
Medical History	X		
Eligibility criteria	X		
Index data collection		X	X
Adverse event evaluation		X	X

11 Statistical Plan

11.1 Sample Size

No formal statistical hypothesis is proposed for this study. A non-statistically driven sample size of 30 patients is considered sufficient for this pilot study.

11.2 Handling of Missing Data

This is a prospective acute outcomes study and therefore we do not anticipate any missing data. In the event of any unexpected missing data, no attempt to impute this missing data will be made. Missing data will simply be treated as missing in the statistical analysis.

12. Safety and Adverse Events

12.1 Definitions

12.1.1 Unanticipated Problems Involving Risk to Subjects or Others (UPIRTSO)

Any unanticipated problem or adverse event that meets the following three criteria:

- Serious: Serious unanticipated problems or events that result in significant harm, (which may be physical, psychological, financial, social, economic, or legal) or increased risk for the subject or others (including individuals who are not research subjects). These include: (1) death; (2) hemorrhage or life threatening adverse experience; (3) hospitalization - inpatient, new, or prolonged; (4) disability/incapacity - persistent or significant; (5) birth defect/anomaly; (6) breach of confidentiality and (7) other problems, events, or new information (i.e. publications, DSMB reports, interim findings, product labeling change) that in the opinion of the local investigator may adversely affect the rights, safety, or welfare of the subjects or others, or substantially compromise the research data, **AND**
- Unanticipated: (i.e., unexpected) problems or events are those that are not already described as potential risks in the protocol, consent document, not listed in the Investigator's Brochure, or not part of an underlying disease. A problem or event is "unanticipated" when it was unforeseeable at the time of its occurrence. A problem or event is "unanticipated" when it occurs at an increased frequency or at an increased severity than expected, **AND**
- Related: A problem or event is "related" if it is possibly related to the research procedures.

12.1.2 Adverse Event

An untoward or undesirable experience associated with the use of a medical product (i.e. drug, device, biologic) in a patient or research subject.

12.1.3 Serious Adverse Event

Adverse events are classified as serious or non-serious. Serious problems/events can be well defined and include:

- death
- hemorrhage
- life threatening adverse experience
- hospitalization
- inpatient, new, or prolonged; disability/incapacity
- persistent or significant disability or incapacity
- birth defect/anomaly

All adverse events that do not meet any of the criteria for serious, should be regarded as non-serious adverse events.

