4.2 Background

Ultrasound-guided percutaneous liver and kidney biopsies are used widely for the diagnosis, staging and follow-up of hepatic and renal disease. Complications of these procedures include pain, bleeding, pneumothorax, bile peritonitis, arteriovenous fistula formation, glomeruli in kidney biopsies, hemorrhage, and others. Of the serious complications, bleeding is the most common, with an incidence ranging from 0.8 percent (%) to 1%, and subsequent fatality may occur in as many as three (3) out of 10,000 liver biopsies. Similarly, the bleeding complications from kidney biopsies have been reported as between 9% to 34%.^{1,2,3} In addition, bleeding from breast biopsies have occurred in incidences ranging from 6.6% to 8.2%, and occurrences of bleeding from lung biopsies range from .6% - 17.6%.⁵

5 Risk Benefit Analysis

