5.1 Risks to the Patient -FMEA

No additional risks are associated with the use of Kronos Electrosurgical Device compared to existing electrocautery devices.

POTENTIAL ADVERSE EVENTS

Possible complications associated with the use of the Kronos device are similar to those associated with electrocautery devices and include, but may not be limited to:

Common (occurs in more than 10% of patients undergoing this type of procedure):

- Pain – study device or standard of care biopsy related
- Hemorrhage/Bleeding – study device or standard of care biopsy related
- Internal and external burn – study device related
- Scarring – study device or standard of care biopsy related

Less Common (occurs in 1-10% of patients undergoing this procedure):

- Reintervention - – study device or standard of care biopsy related

Rare (occurs in less than 1% of patients undergoing this type of procedure):

- Allergic Reaction – study device or standard of care biopsy related
- Inflammatory Response - – study device or standard of care biopsy related
- Infection - study device or standard of care biopsy related
- Death - study device or standard of care biopsy related
- Interference with implantable device – study device related

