5.2 Potential Benefits to the Patient

Reduction or prevention of bleeding following a biopsy procedure could prevent the need of hospitalization, blood transfusion and sometimes surgery or another procedure to stop the bleeding.

6 Study Objectives

The objective of this study is to verify the in-animal models evaluated optimal withdrawal parameters in humans to reduce and control bleeding following a biopsy procedure and to assess preliminary usability evaluations of the Kronos Electrosurgical Device.

7 Study Design

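### Section 12.1.3 makes any adverse event recorded as hemorrhage serious whatever its consequence, so the SAE count reviewed under 12.4 would consist largely of expected bleeding

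*Combined protocol and SAP*

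**What the plan says.** Section 12.1.3 introduces the seriousness criteria with "Serious problems/events can be well defined and include". Hemorrhage is a separate item in the list, next to death, life-threatening experience and hospitalization, and carries no condition on amount, treatment or outcome. The section closes with "All adverse events that do not meet any of the criteria for serious, should be regarded as non-serious adverse events". Read literally, an adverse event recorded as hemorrhage can therefore never be non-serious.

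Section 12.1.1 has a parallel item, "2) hemorrhage or life threatening adverse experience". It stands under a lead-in about significant harm or increased risk, and a UPIRTSO must also be unanticipated and related.

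Section 5.1 lists "Hemorrhage/Bleeding – study device or standard of care biopsy related" as a single item under "Common (occurs in more than 10% of patients undergoing this type of procedure". Section 4.2, in a paragraph on liver and kidney biopsy, gives the rate of bleeding as a serious complication: "Of the serious complications, bleeding is the most common, with an incidence ranging from 0.8 percent (%) to 1" percent. Section 5.2 says that less bleeding "could prevent the need of hospitalization, blood transfusion and sometimes surgery or another procedure to stop the bleeding".

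The severity scale in 12.3.1 has a mild grade for events that need no special treatment. Section 12.2 requires immediate reporting of SAEs that are at least possibly related. Section 12.4 bases medical monitoring on how many SAEs occur and of what type.

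**The concern.** Safety is part of the primary objective in the Study Summary, and the SAE tally is the one measure that 12.4 names for medical monitoring. If the definition is followed to the letter, a bleed that is graded mild and left untreated enters that tally beside a life-threatening one. Because 5.1 expects bleeding in more than one patient in ten, such events could make up most of the tally.

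The protocol neither equates minor access-site bleeding with hemorrhage nor separates the two. With up to 5 sites and no shared rule, one site may record a small bleed as a hemorrhage, and so as an SAE, while another does not.

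The list is also too narrow in one place. It has no criterion for an event that needs an intervention. A burn that leads to reintervention without admission is non-serious unless it meets another item. Yet 5.1 lists burns as common and reintervention at 1-10%, and the secondary outcomes in 7.4 include absence of reintervention.

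**Working it through.** The plan states no expected SAE count, and section 11.1 says that the sample size of 30 is not statistically derived, so there is no figure to reproduce. The steps below show what the definition implies at the documents' own rates.

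**Inputs.** n = 30 (11.1) and n = 20 (minimum accrual, 8.3). Bleeding of any kind: 10%, the floor of the class in 5.1, which has no upper limit. Bleeding as a serious complication: 0.8% to 1% (4.2).

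**Expected count and chance of at least one event.** Expected = n × p; P(at least one) = 1 − (1 − p)^n.

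- All bleeding, n = 30: 30 × 0.10 = 3.0; 1 − 0.90^30 = 95.8%.
- All bleeding, n = 20: 20 × 0.10 = 2.0; 1 − 0.90^20 = 87.8%.
- Serious bleeding, n = 30: 30 × 0.008 = 0.24 to 30 × 0.01 = 0.30; 1 − 0.992^30 = 21.4% to 1 − 0.99^30 = 26.0%.
- Serious bleeding, n = 20: 20 × 0.008 = 0.16 to 20 × 0.01 = 0.20; 14.8% to 18.2%.

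If both rates applied to the same patients, (3.0 − 0.3)/3.0 = 90% of hemorrhage SAEs would be of the expected, non-dangerous kind.

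**Dilution of a signal.** The plan has no flagging rule, so the following are assumptions:

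- Dangerous bleeds have a 1% background rate and form part of all bleeds.
- The all-bleed background is 10% or 20%.
- The dangerous rate rises to 5% or 10% while other bleeds stay constant. The all-bleed rate then becomes, for example, 10% − 1% + 10% = 19%.
- A flag is raised at the smallest count whose exact one-sided binomial level is at most 0.05.

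Chance of a flag:

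| n | Dangerous rate | Dangerous bleeds counted separately | All bleeds, 10% background | All bleeds, 20% background |
|---|---|---|---|---|
| 30 | 10% | 81.6% | 34.0% | 23.1% |
| 30 | 5% | 44.6% | 11.7% | 8.3% |
| 20 | 10% | 60.8% | 32.7% | 19.8% |
| 20 | 5% | 26.4% | 13.7% | 8.3% |

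Flags for n = 30 are at 2, 7 and 11 events (levels 0.036, 0.026, 0.026). For n = 20 they are at 2, 5 and 8 events (levels 0.017, 0.043, 0.032). The levels differ because counts are discrete, and this explains part of the gap at n = 30. At n = 20 the undivided count has the more lenient rule and still detects less often, so the direction does not depend on this.

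**The case against.** **The information to separate the bleeds is collected.** This stands. Every adverse event gets a severity grade, and its description, relationship and any intervention are recorded (12.3.1). Life-threatening events and hospitalization are separate criteria (12.1.3), access-site blood is weighed (10.2), and 12.4 looks at the type of SAE as well as the number. With at most 30 patients and descriptive reporting, bleeds can be read case by case. A reader might infer that the SAE count cannot show a safety signal. The documents do not support that, and the table shows reduced detection, not none. What remains is that no section says the bleeds will be separated, and severity is a different attribute from seriousness.

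**Blood on gauze is not an SAE.** This also stands. An event must first be an adverse event as defined in 12.1.2, and the weighing in 10.2 measures an outcome. It would be wrong to infer that every patient with access-site bleeding has an SAE. The point concerns events that are recorded as hemorrhage.

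**Section 12.1.1 is not open to the same criticism.** Correct. Its harm-or-risk lead-in and its unanticipated and related conditions limit it. The inconsistency is that 12.1.3 lacks the lead-in.

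**The bare item may be a drafting slip.** The list in 12.1.3 looks like the items of 12.1.1 broken partway, so hemorrhage may be half of one item. This cannot be proved. Rejoining the halves would still leave hemorrhage as an alternative to a life-threatening experience, with no consequence attached.

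**The rule may be deliberate caution.** Calling every hemorrhage serious is a defensible choice in a feasibility study of a device meant to control bleeding. The protocol does not say that this is the intention. It is a reason to leave the reporting of minor bleeds to the sponsor, but not a reason to leave the count undivided.

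**Conclusion.** The definition should be corrected. As written, the SAE number under 12.4 would consist largely of expected bleeding: at least 3.0 hemorrhage SAEs expected in 30 patients at the 10% floor, with a 95.8% chance of at least one. This assumes that investigators record such bleeding as an adverse event called hemorrhage, which the text neither requires nor excludes. A signal of dangerous bleeds is weakened but not lost. The detection figures are illustrative, since they rest on assumed rates and on a rule that the plan does not contain.

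A reader might divide 3.0 by 0.30 and infer that the SAE count changes tenfold through the reading of one word. The documents do not support this. The class in 5.1 covers all organs and bleeding from device or biopsy, while 0.8% to 1% comes from a liver and kidney background paragraph. The ratio therefore mixes organ and cause with definition.

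The missing intervention criterion is a narrower gap. A bleed that needs transfusion or a procedure is already serious as a hemorrhage, so only non-bleeding events handled without admission fall outside. Those are still recorded through the secondary outcome and the adverse event worksheet.

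The primary endpoint in the Study Summary depends on procedure-related adverse events of any seriousness, so it is not affected.

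**What to change.** - Reconcile 5.1, 12.1.1 and 12.1.3 so that a hemorrhage counts as serious because of its consequence. The sponsor can start from the significant-harm lead-in of 12.1.1 and the consequences that 5.2 already names. The choice of criterion is the sponsor's.
- Apply the same intervention criterion to all adverse events, so that a reintervention without admission is classified in the same way whether or not the event is a bleed.
- Keep recording and grading every bleed that is an adverse event.
- For the review under 12.4, tabulate hemorrhages by seriousness, severity grade and whether an intervention was needed.

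The cost is wording in a few sections, a change to the SAE form and one descriptive table from fields already collected. The debatable consequence is that minor bleeds could leave the immediate-reporting stream of 12.2. The sponsor must decide whether they stay in it and say so in the protocol. The tabulation is useful either way.

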12.1.4 Adverse Event Reporting Period

For this study, the follow-up period is defined as up to 30 days post-procedure.

12.1.5 Preexisting Condition

A pre-existing condition is one that is present before the start of the study. A pre-existing condition should be recorded as an adverse event if the frequency, intensity, or the character of the condition worsens during the study period.

12.2 Recording of Adverse Events

At each contact with the subject, the study team must seek information on adverse events by specific questioning and, as appropriate, by examination. Information on all adverse events should be recorded immediately in the source document, and also in the appropriate adverse event section of the electronic case report form (CRF). All clearly related signs, symptoms, and abnormal diagnostic, laboratory or procedure results will be recorded in the source document.

All adverse events occurring during the study period must be recorded. The clinical course of each event should be followed until resolution, stabilization, or until it has been ultimately determined that the study treatment or participation is not the probable cause. Serious adverse events that are still ongoing at the end of the study period must be followed up, to determine the final outcome. Any serious adverse event that occurs during the Adverse Event Reporting Period and is considered to be at least possibly related to the study treatment or study participation should be recorded and reported immediately.

12.3 Reporting of Serious Adverse Events and Unanticipated Problems

When an adverse event has been identified, the study team will take appropriate action necessary to protect the study participant and then complete the appropriate documentation. The site's Principal Investigator will evaluate the event and determine the necessary follow-up and reporting required.

12.3.1 Principal Investigator reporting notifying the IRB

The site's Principal Investigator will report to the IRB any UPIRTSOs and Non-UPIRTSOs according to the IRB Policy and Procedures. Any serious adverse event (SAE) which the Principal Investigator has determined to be a UPIRTSO will be reported to the IRB as soon as possible but no later than 5 working days after the investigator first learns of the problem/event.

The following information will be collected on the adverse event worksheet (and entered in the research database):

- Study ID
- Disease
- The date the adverse event occurred
- Description of the adverse event
- Relationship of the adverse event to the research device*
- Determination if the adverse event was expected
- The severity of the adverse event (severity scale described below**)
- If any intervention was necessary
- Resolution (was the incident resolved spontaneously, or after discontinuing treatment)
- Date of Resolution

The site's Principal Investigator will review all adverse event reports to determine if specific reports need to be made to the IRB and FDA. The site's Principal Investigator will sign and date the adverse event report when it is reviewed. For this protocol, only directly related SAEs/UPIRTSOs will be reported to the IRB.

* Relationship Index

The relationship of an AE to the Investigational Device is a clinical decision by the site's Principal Investigator based on all available information at the time of the completion of the CRF's and is graded as follows:

1. Not related: a reaction for which sufficient information exists to indicate that the etiology is unrelated to the study device.

2. Unlikely: a clinical event, including laboratory test abnormality, or underlying disease provide plausible explanations.
3. Possible: a clinical event, including laboratory test abnormality, with a reasonable time sequence to use of study device but which could also be explained by concurrent disease or other drugs/devices or chemicals.
4. Probable: a clinical event including laboratory test abnormality, with a reasonable time sequence to use of the device, unlikely to be attributed to concurrent disease or other devices or chemicals.
5. Definite: a reaction that follows a reasonable temporal sequence from use of the device.

** Severity Scale

The maximum intensity of an AE should be graded according to the definitions below and recorded in detail as indicated on the CRF. If the intensity of an AE changes over a number of days, then separate entries should be made having distinct onset dates.

1. Mild: AEs are usually transient, requiring no special treatment, and do not interfere with patient's daily activities.
2. Moderate: AEs typically introduce a low level of inconvenience or concern to the patient and may interfere with daily activities but are usually ameliorated by simple therapeutic measures.
3. Severe: AEs interrupt a patient's usual daily activity and traditionally require systemic drug therapy or other treatment.

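### Section 12.3.1 gives IRB reporting rules that conflict on their natural reading, because a closing sentence limits reports to undefined *directly related* events; the grade *Definite* also lacks a condition on other causes

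*Combined protocol and SAP*

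**What the plan says.** Section 12.3.1 contains three statements about what goes to the IRB.

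- Opening sentence: the site's Principal Investigator "will report to the IRB any UPIRTSOs and Non-UPIRTSOs according to the IRB Policy and Procedures".
- Second sentence: an SAE "determined to be a UPIRTSO will be reported to the IRB as soon as possible but no later than 5 working days" after the investigator learns of it. No further limit on relatedness is stated.
- Last sentence of the body text, before the relationship and severity scales: "For this protocol, only directly related SAEs/UPIRTSOs will be reported to the IRB".

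Section 12.1.1 defines a UPIRTSO by three elements: serious, unanticipated and related. The third is met if the event is "possibly related to the research procedures".

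Section 12.2 covers SAEs in the reporting period that are "considered to be at least possibly related to the study treatment or study participation should be recorded and reported immediately". It does not say to whom.

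The relationship scale in 12.3.1 has five grades: Not related, Unlikely, Possible, Probable and Definite. It grades relation to the device: "The relationship of an AE to the Investigational Device is a clinical decision" of the site's Principal Investigator.

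**The concern.** *Directly related* reads as a stricter test than *possibly related*, and the opening words of the closing sentence invite a site to treat it as the rule that controls this study. One site could then hold back from the IRB a possibly related UPIRTSO that another site, following the 5-working-day sentence, would report.

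Uncertain attribution is to be expected here. Section 5.1 lists 10 potential events and attributes 8 of them to either the study device or the standard-of-care biopsy. Events on that list count as unanticipated only if they are more frequent or more severe than expected. The same overlap between device and biopsy could, however, make attribution of an unlisted event uncertain too. Safety is part of the primary objective in the Study Summary, and 12.3 and 12.3.1 name only the IRB and FDA as recipients of reports.

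Separately, the top grade of the causality scale appears easier to meet than the grade below it.

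**Working it through.** The plan gives no figure to reproduce, and Section 11.1 proposes no hypothesis. The check is a comparison of wording.

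**Step 1. Which events the 5-working-day rule covers.** The rule applies to any SAE judged a UPIRTSO. By 12.1.1, a possible relation to the research procedures satisfies the relatedness element. A serious, unanticipated, possibly related SAE is therefore due at the IRB within 5 working days. The definition and the rule form one chain, since 12.1.1 affects reporting only through the rule that uses it.

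**Step 2. What the closing sentence does.** Its grammar leaves open whether the qualifier applies to both nouns or only to the first. This step assumes the ordinary sense, in which *directly* is narrower than *possibly*.

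| Event | Opening and second sentences | Qualifier on both nouns | Qualifier on SAEs only |
|---|---|---|---|
| SAE judged a UPIRTSO, possibly but not directly related | Due within 5 working days | Excluded: conflict | Still due: no conflict |
| Non-UPIRTSO that is not a directly related SAE | As IRB policy requires | Excluded: conflict if policy requires a report | Excluded: conflict if policy requires a report |

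The first row conflicts on one reading. The second row can conflict on both, but its size depends on local policies that are not in the documents.

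**Step 3. Whether the term can be looked up.** It is defined nowhere and matches none of the five grades. The scale could not supply it cleanly, because it grades relation to the device. The 12.1.1 test is relation to the research procedures, and its list of serious problems includes breach of confidentiality, which a device-causality scale cannot grade.

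**Step 4. Whether 12.2 resolves it.** It uses the wider test, at least possibly related, and asks for immediate reporting. Because it names no recipient, it sets no IRB rule and cannot settle which sentence of 12.3.1 governs.

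**Step 5. The top of the causality scale.**

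| Grade | Timing condition | Condition on other causes |
|---|---|---|
| Possible | Reasonable time sequence | Could also explain the event |
| Probable | Reasonable time sequence | Unlikely to explain the event |
| Definite | Reasonable temporal sequence | None |

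An event that meets *Possible* or *Probable* already meets the only stated condition of *Definite*. *Definite* does call the event a reaction, but that adds no causal test, since the bottom grade uses the same word: "Not related: a reaction for which sufficient information exists to indicate that the etiology is unrelated to the study device".

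**The case against.** The strongest reply is grammatical: if the qualifier belongs to SAEs alone, every UPIRTSO remains reportable and the clash with the 5-working-day rule and 12.1.1 disappears. The sentence does not rule this out, so that much stands. It leaves the term undefined and the word *only* at odds with the opening duty on Non-UPIRTSOs.

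A second reply is that other provisions protect against under-reporting. Under 12.3 the investigator evaluates each event and decides what reporting is needed. Under 12.3.1 the investigator reviews all adverse event reports for IRB and FDA reporting, and 12.4 calls for a site data and safety-monitoring plan. The opening sentence also places both UPIRTSOs and Non-UPIRTSOs under IRB policy. These bear on how likely a missed report is. They do not say which sentence controls, and they leave the decision to each site.

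Three stronger readings may tempt a reader, and the documents do not support them.

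- That 12.1.1 and 12.2 are further IRB thresholds outnumbering the closing sentence. The first is a definition that acts through the 5-working-day rule, and the second names no recipient.
- That the loss can be sized by counting the relationship grades that would drop out. No text maps the term to the grades, and the scale concerns the device only.
- That the wording of *Definite* distorts a result. No endpoint or stated reporting threshold uses the boundary between *Probable* and *Definite*, Section 11 specifies no causality tabulation, and grading is left to clinical judgement on all available information.

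**Conclusion.** The point holds, with moderate confidence. Section 12.3.1 needs correcting as written. On the natural reading, its closing sentence excludes from IRB reporting some events that its second sentence makes due within 5 working days. On the narrower reading, it still applies an undefined limit that sits against the opening sentence. The conclusion assumes that *directly* is stricter than *possibly* and, for the conflict over UPIRTSOs, that the qualifier covers both nouns.

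A reader might infer that the rules contradict each other on every reading, or that reportable events will be missed. The documents establish neither. The first depends on grammar that the sentence leaves open. The second depends on site practice and local IRB policy. No count of affected patients or reports can be given, because the documents state neither how often UPIRTSOs are expected nor how many would fall short of a direct relation. No endpoint result changes; what is at stake is consistent safety oversight across up to 5 sites.

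The point about *Definite* is sound but secondary, and is a wording correction only.

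**What to change.** Delete the closing sentence of the 12.3.1 body text, or reconcile it with 12.1.1 and the 5-working-day rule, so that one stated threshold of relatedness to the research procedures governs IRB reporting at every site. Do not borrow that threshold from the five-grade scale, which grades relation to the device only.

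As a secondary change, add to *Definite* a condition on other causes, for example that no other cause is plausible, so that it is at least as strict as *Probable*.

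The cost is a wording amendment to one section, with no effect on sample size or analysis. Whether the number of IRB reports would change cannot be estimated from the documents.
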